- c. Objectives: Healthy People 2020 identified sexual/gender minority (SGM) older adults as a health disparate population. The lack of efficacious research-based interventions for such vulnerable older adults with Alzheimer's disease and related dementias (AD/RD) is a significant public health problem. AD/RD will affect up to four million SGM older adults by 2050.^{1,2} SGM older adults are at elevated risk of social isolation and experience significant barriers to healthcare access.³ Existing interventions for older adults with dementia have been found to be effective for caregiving dyads.⁴ Yet, SGM older adults, compared to heterosexuals, are significantly less likely to be married or to have biological family members to support them,¹ and a significant proportion of SGM older adults living with dementia have no caregiver or care network.⁵ The goal of the proposed research is to design and pilot test an innovative translation of a modified version of Reducing Disability in Alzheimer's Disease (RDAD) to support those living with dementia without a family caregiver, directly addressing unique SGM-specific risk factors for sustainable and comprehensive dementia care including social stigma, marginalization, identity management, and increased need for social support. Given that the RDAD^{6,7} has been evaluated in a randomized controlled trial and has shown to successfully train community-dwelling care-recipient (CR) and care-giver (CG) dyads to increase the physical activity and functioning of individuals with AD/RD and their CGs and to teaches CGs techniques for managing behavioral symptoms of CRs, this study adds a modification that will provide an intervention for SGM older adults with AD/RD without caregivers. Building on the success of two previous NIH-funded studies (NHAS: 2R01 AG026526; [name], PI; RDAD: R01 AG10845; [name], PI), we will address the following aims: Aim 1. Develop a personalized RDAD intervention (hereafter referred as Personalized Care Network suitable for SGM older adults living with dementia without caregivers; Aim 2. Implement a preliminary randomized controlled trial (RCT) of 30 participants with 2 arms (routine medical care vs. the Personalized Care Network approach) to assess the acceptability, feasibility, and initial efficacy of the intervention.
- d. Study design: This study will utilize a 2-group randomized controlled trial design including two assessments, i.e. a pre-treatment and a post-treatment

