- b. Inclusion criteria: 1) 50 years of age or older at enrollment; 2) sexual or gender minority; 3) has early stage dementia including Alzheimer's disease; 4) lives in the community (not in a care facility). Based on the definition of dementia suggested by Alzheimer's Association and scientific literature, dementia will be determined by asking of potentially participating individuals 1) their current diagnostic status of AD/RD or 2) any difficulties in the domains of dementia AND any help needed with complex daily activities. This method has two positive aspects: (1) it precludes considerable increased costs that would be necessitated by providing a physical exam and (2) avoids unnecessary delays (and potentially loss of subjects) by scheduling an exam or waiting for receipt of patient charts.
- c. Exclusion criteria: 1) Have plans to move to a long-term care setting within 6 months of enrollment; 2) have a known terminal illness (with death anticipated within the next 12 months); 3) have had a hospitalization for a psychiatric disorder in the 12 months prior to baseline; 4) to be actively suicidal, hallucinating, or delusional; 5) have any physical limitations/chronic conditions preventing participation in an exercise program and 6) have more than early stage dementia. More than early stage dementia will be determined by 1) their current diagnostic status of AD/RD or 2) having difficulties in more than one cognitive domain AND significant difficulty in simple daily activities such as bathing, dressing, grooming, using the shower, transferring from bed to chair, using the telephone, or doing minor household chores. The final exclusion criteria will allow us to exclude individuals with severe cognitive impairment from the study.
- d. Number of subjects

Group name/description	Maximum desired number of individuals (or other subject unit, such as families) who will complete the research
Personalized Care Network	15 individuals with early stage memory loss
RMC (Routine medical care)	15 individuals with early stage memory loss

3. Recruiting and Screening Participants

- a. Recruiting and screening:

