c. **Interventions:** For the **Personalized Care Network group**, the intervention will be done virtually using a video conferencing platform such as Zoom. Two coaches will meet with 4-6 individuals for 9 one-hour sessions over six weeks. We will use the treatment manual developed and used for an earlier translational research (IRB STUDY00003076, Title: Older Adults Living with Alzheimer's Disease and their Caregivers, PI: [name]). The manual was modified in March 2020 in order to transition from an in-home intervention to a virtual intervention. The manual includes text for the coaches, graphic illustrations of exercises, handouts, and process/treatment fidelity forms. A video link demonstrating exercises will be provided to participants. The coaches will encourage and help participants with their exercises, and develop plans to address difficult behaviors. The exercise component includes seated exercises with aerobic/endurance activities, strength training, and exercises to improve balance and flexibility. Exercises are introduced incrementally and individualized to meet the needs of each person. Each exercise is first demonstrated by the coach, then practiced by the participants. Coaches monitor the exercises closely in order to ensure that they are practiced safely and correctly. In the behavior management component, the ABC technique is applied. Study participants are taught to identify the antecedent (A) to a behavioral issue or problem (B) as well as the consequences (C) of the behavior. Participants are instructed to identify and modify behavioral problems that can impair day-to-day function and interfere with exercise participation. They are given specific training in how to identify precipitants of problem behaviors, and how to modulate their own responses to these problems. Participants are also encouraged to identify pleasant activities that can be incorporated into the exercise program. An Exercise Coach will meet via a video conferencing platform individually with each treatment group participant once a week for 6 weeks to ensure exercises are done safely and correctly. Participants in the treatment group will be invited to participate in a focus group after their post treatment assessment is completed.

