d. Participants in the **RMC group** will use the same routine medical care they are currently using as needed. Exercise and behavioral management training will not be provided to the RMC group. An online workshop will be offered to RMC participants after their post assessment. The workshop will focus on aging, memory loss and maximizing health and independence.

e. **Post-treatment assessments:** The UW research staff will conduct, via telephone, a post-treatment assessment after all sessions are completed to evaluate treatment effectiveness outcomes for participants. Participants will receive \$25 for each assessment.

5. Outcome Measure(s):

a. Change in Physical Activity [Time Frame: Baseline (pre-treatment) and 7 weeks (post-treatment)]

- Minutes spent on exercising per week in the past month were calculated from the following two questions: (1) How much time did you spend on exercises (hours per day) on a typical day during the last month; (2) How many days did you spend on exercises during the last month.

- b. Change in Physical Functioning [Time Frame: Baseline (pre-treatment) and 7 weeks (post-treatment)]
 - Physical functioning subscale of SF-36 (Medical Outcomes Study [MOS] 36-Item Short Form), consisting of 10 items assessing if participants' health limit them in activities such as walking, climbing, lifting, etc. on a 3-point scale ranging from 'yes, limited a lot' to 'no, not limited at all.'
- c. Change in Quality of Life [Time Frame: Baseline (pre-treatment) and 7 weeks (post-treatment)]
 - Quality of Life-AD scale assessed via interviews with participants, consisting of 13 items with a 4-point response scale (1 = poor to 4 = excellent) asking about their feeling about different aspects of life. Summary scores are a sum of the 13 items.

6. Identifiability of data

- a. Each and every subject will be assigned a unique identification number. This number serves as an indirect link between the assessment data collected and any identifying information gathered as a part of the study. Only the PIs and authorized research staff will have access to the link between data and the direct identifiers.
- b. Participants' name and their contact information (home address, email address, phone numbers) will be accessed by research staff to contact participants regarding the intervention and to schedule pre and post treatment assessments with participants.

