- c. Protections against physical discomfort: If subjects experience mild physical discomfort related to engaging in new physical exercise activities, they will be informed that they do not need to participate in any exercises. We estimate physical discomfort to be minimal in the proposed study.
- d. A potential breach of confidentiality regarding subjects' sexual/gender identity and/or medical condition may cause psychological or social harm. All team members have signed a confidentiality agreement prior to being involved in the study. All participant information is to be kept strictly confidential with the only exception being incidents of abuse of a dependent adult or minor child and risks of imminent harm to others or to the subject. All researchers have completed training in research with human subjects.

10. Analysis plan

- a. The point estimates of the proportions of eligible participants who agree to participate in the study and enrolled participants who comply with exercise assignments and adhere to the program sessions will be computed to test enrollment feasibility and intervention acceptability. Data from all measures at each time point will be examined utilizing univariate statistics in which psychometric properties of each variable will be determined. While random assignment is expected to produce comparable intervention groups, this will be ensured by comparing demographic characteristics and outcomes of interest at the baseline across intervention groups. To test initial efficacy of the Personalized Care Network approach and RMC on primary outcomes, we will use ANCOVA, which helps to reduce error variance, yielding a more powerful test. The proposed sample size is sufficient to detect a medium effect of the preliminary intervention,⁸ which is greater than a clinically important difference level.⁹ We will compute and assess confidence intervals to evaluate precision of sample estimates and effect sizes for each outcome variable so as to derive proper sample size for the next stage of the study.

References

1. [name] KI, Kim H-J, Barkan SE, Muraco A, Hoy-Ellis CP. Health disparities among lesbian, gay, and bisexual older adults: Results from a population-based study. *American Journal of Public Health*. 2013;103(10):1802-1809.

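### Only the Personalized Care Network arm is treated in groups, and neither the ANCOVA nor the planned sizing of the next stage allows for correlation within those groups

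*Combined protocol and SAP*

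**What the plan says.** Section 4c describes delivery in the Personalized Care Network arm: "Two coaches will meet with 4-6 individuals for 9 one-hour sessions over six weeks". It adds a weekly one-to-one video session with an exercise coach for six weeks. Section 4d leaves the comparator untreated: "Exercise and behavioral management training will not be provided to the RMC group". The RMC workshop comes after the post assessment, so it cannot affect the outcomes.

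Section 4a allocates 15 participants to each arm. Section 2d gives 15 per arm under the column heading "Maximum desired number of individuals (or other subject unit, such as families) who will complete the research", so 15 is a ceiling on completers.

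For efficacy, section 10a states that "we will use ANCOVA, which helps to reduce error variance, yielding a more powerful test". It closes by planning confidence intervals and "effect sizes for each outcome variable so as to derive proper sample size for the next stage of the study". No group or coach term, ICC, random effect, robust variance or design effect appears anywhere in the document.

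**The concern.** Members of a treated group share two coaches, the same live practice and the same behavior-management sessions. Their outcomes may therefore be more alike than those of two RMC participants. ANCOVA assumes independent residuals. If the treated residuals are positively correlated within groups, the treated-arm mean is less precise than the ANCOVA reports, and the error runs towards overstated precision.

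Aim 2 is "to assess the acceptability, feasibility, and initial efficacy of the intervention". Acceptability and feasibility are untouched. At stake are the efficacy intervals and the use of precision and effect sizes to plan the next trial. If that calculation also leaves out a design effect, the next trial falls short of its intended power.

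**Working it through.** **Inputs from the document.** 15 per arm (4a); groups of 4-6 in one arm only (4c, 4d); ANCOVA (10a). Two groups hold at most 12 people and four need at least 16, so 13-15 treated people make three groups, 8-11 make two, and 12 make two or three.

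**Assumptions, because the document is silent.** Groups stay fixed over the nine sessions (the natural reading, but not stated). Baseline values are not clustered. ICC is 0.01, 0.05 or 0.10 as a share of total outcome variance. The baseline-post correlation *r* is 0, 0.5 or 0.7. For the next stage: effect d = 0.5 SD, two-sided 5%, 80% power, groups of 5. The plan gives no figure for clustering to reproduce.

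**1. Type I error of the ANCOVA.** Simulated null trials, one baseline covariate, 200,000 per cell, three groups of 5 against 15 (27 df), nominal 5%:

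| ICC | r = 0 | r = 0.5 | r = 0.7 |
|---|---|---|---|
| 0 | 5.0% | 5.0% | 5.0% |
| 0.01 | 5.3% | 5.3% | 5.4% |
| 0.05 | 6.2% | 6.6% | 7.3% |
| 0.10 | 7.3% | 8.1% | 9.7% |

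The mean estimated difference is within 0.002 SD of zero in every cell, so there is no bias. The rise with *r* comes from the ICC convention: ICC 0.10 of total variance at r = 0.7 is 0.10/(1 − 0.49) = 0.196 of residual variance. With ICC defined on residual variance, the figures are about 5.2%, 6.2% and 7.3% at any *r*. With two groups of 6 against 12, ICC 0.10 of total variance gives 7.9%, 8.9% and 10.9%.

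**2. Interval width.** Expected half-width in outcome SDs, ignoring chance baseline imbalance, is t(0.975, 27) × √{[2(1 − r²) + (m − 1)·ICC]/15} with m = 5:

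- r = 0: 0.749 at ICC 0, then 0.757, 0.786 and 0.821.
- r = 0.7: 0.535 at ICC 0, then 0.545, 0.585 and 0.631.

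The correct interval is 1-2%, 5-9% and 10-18% wider than the one the ANCOVA would give.

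**3. Next-stage size.** n per arm = (z_α/2 + z_β)² × [2(1 − r²) + (m − 1)·ICC]/d² = 7.849 × [2(1 − r²) + 4·ICC]/0.25. Take r = 0 if no credit is given for baseline adjustment. Example at r = 0, ICC 0.10: 7.849 × 2.4/0.25 = 75.3, so 76.

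| r | n per arm, ICC 0 | 0.01 / 0.05 / 0.10 | Power if the ICC 0 size is kept |
|---|---|---|---|
| 0 | 63 | 65 / 70 / 76 | 79 / 76 / 73% |
| 0.5 | 48 | 49 / 54 / 60 | 80 / 76 / 71% |
| 0.7 | 33 | 34 / 39 / 45 | 80 / 74 / 67% |

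If the size is reduced by (1 − r²) for ANCOVA, the design effect must be scaled too. At ICC 0.10, using 1 + (m − 1)·ICC unscaled in the treatment arm gives 57 per arm at r = 0.5 (power 78.2%) and 39 at r = 0.7 (power 74.5%), both short of 80%.

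**The case against.** The best case against has four parts.

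*The ICC is unknown and may be small.* Individualized exercises, weekly one-to-one coaching and individual telephone assessments could all dilute correlation. This stands: at ICC 0.01 the effect is negligible. But the one-to-one sessions are added to the nine group sessions and do not replace them.

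*The pilot's own imprecision is larger.* On 27 df the half-width varies by about 14% (coefficient of variation) by chance. A variance estimate has a 95% range of 0.63 to 1.85 times its value, so 63 per arm could be about 39 to 116. This also stands, and it limits the weight of the point. However, chance error goes both ways, while omitting a positive ICC always understates the need.

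*The direction could reverse.* If participants were randomized within enrolment waves and the correlation came from timing shared by both arms, ANCOVA would be conservative: with three waves of 5 + 5, type I error is roughly 4.4-4.6% at ICC 0.05 and 3.7-4.2% at 0.10. The document describes no such randomization, so this remains a possibility only. The concern here is correlation arising within treated groups.

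*The next-stage calculation has not been made.* True. Section 10a gives no formula and rules nothing out, so the plan contains an omission and no arithmetic error. The power losses apply only if the omission is carried forward.

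**Conclusion.** The point holds, conditionally. One arm is grouped, the other is not, and the analysis plan does not recognize it. If treated groups are fixed and the within-group ICC is positive, the ANCOVA intervals are too narrow. The effect is nil at ICC 0, negligible at 0.01 and modest at 0.10. The largest type I error for three groups of 5 (9.7%) depends on a high baseline correlation and on defining ICC against total variance; against residual variance it is about 7.3%. The treatment estimate is sound, and the feasibility and acceptability aims are unaffected. The change is worth making because it is cheap and the plan states that precision will inform the next trial. It is not a fault that invalidates the pilot.

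**What to change.** 1. Name each treated participant's group and coaches as analysis variables. They may be recoverable from the adherence data, since the proportion of "enrolled participants who comply with exercise assignments and adhere to the program sessions will be computed", or from the session forms ("The manual includes text for the coaches, graphic illustrations of exercises, handouts, and process/treatment fidelity forms"), but the plan does not say so. State whether groups stay fixed.
2. Keep the baseline-adjusted ANCOVA. Beside it, report for each outcome a sensitivity interval at ICC 0.01, 0.05 and 0.10: add s² × (m − 1) × [ICC/(1 − r²)]/n_T to the squared ANCOVA standard error and keep the ANCOVA degrees of freedom. Here s² is the ANCOVA residual variance, r² the squared pooled within-arm baseline-post correlation, n_T the number treated, and m the sum of squared group sizes divided by n_T. In simulation with r² estimated from the data, this brings type I error to 4.9-5.1% for three groups of 5 when the assumed ICC is true. A partially nested mixed model is optional and supportive only, because about three groups estimate an ICC poorly.
3. When sizing the next stage, apply a treatment-arm design effect over the same ICC range: 1 + (m − 1)·ICC with no credit for baseline adjustment, or 1 + (m − 1)·ICC/(1 − r²) if the size is reduced by (1 − r²).

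**Cost.** One data field and a few lines of analysis, with no extra pilot participants or visits. The intervals widen slightly, and the next stage needs 1 to 13 more per arm in the examples above. The range of ICC is assumed, not estimated. If the true ICC is 0, the sensitivity interval is conservative: type I error is 4.6-4.8%, 3.2-4.1% and 2.1-3.2% at assumed ICC 0.01, 0.05 and 0.10.

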- d. Consent for recruiting and screening: Potential participants will be asked to contact the UW research team directly after learning about the study. 1) When a potential participant contacts the research team: A UW research staff will describe the study. If the potential participant is interested in participating in the study and determined to have decision making capacity, the research staff will ask if they are willing to voluntarily answer questions assessing eligibility over the phone and will be informed that they can refuse to answer any questions.

4. Study procedures:
 - a. A total of 30 individuals with early stage memory loss will be recruited from Washington, Oregon and California and randomly assigned to one of two groups: Personalized Care Network (n=15) or RMC (n=15).
 - b. Pre-treatment (baseline) assessment: The UW research staff will contact the 30 participants to schedule a pre-treatment assessment via telephone. They will complete

a 40-minute telephone assessment with either the study research coordinator or research study assistant.

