- c. The direct subject identifiers will be stored in a password-protected computer in an encrypted file. Any physical copies of direct identifiers (such as consent forms) will be stored in a secured and locked cabinet. Only the PIs and authorized research staff will have access to the link between data and the direct identifiers. Only the PIs and authorized research staff will have keys to the cabinet.

7. Consent

- a. Consent process: Once interested participants have been identified, eligibility criteria met, and they have agreed to a consent visit, the study assessment staff will schedule a virtual consent visit using Zoom. The UW office will also mail or email the consent form prior to the consent visit so the participant may review it. An electronic consent will be sent to the participants through REDCap. During the consent visit the staff person will ask the participant if they read their consent form. If not, the staff person will ask them to read the forms, or if they would like staff person to read their consent form out loud.
- b. Comprehension: after the consent form has been read the staff person will ask if they have any questions and answer all of their questions. Before signing the consent, the staff person will check in with the participants: 1) whether they understand the consent form; 2) whether they have asked all of their questions and have had enough time to discuss the study; 3) whether they have received satisfactory answers to all their questions; 4) whether they have received enough information about study to decide if they want to participate; 5) whether they understand that they are free to leave the study at any time without having to give a reason and without affecting their medical care. When the participant demonstrates an understanding of the study, they will be asked to

electronically sign the consent using a touch screen on an electronic device and to submit the consent.

- c. Ongoing process: Each session of the interventions and the assessments will be preceded by a brief review of the participants' rights, including their right to withdraw from the study and the right to refuse to answer any questions
- d. Documentation of consent will be obtained for all of the research procedures.
- e. Cognitively impaired adults and other adults unable to consent:

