 - This study includes participants with early stage memory loss who will be able to consent for themselves. Potential participants who cannot consent for themselves will not be included in the study.

8. Privacy and Confidentiality

- a. Privacy protections: Only UW research staff members will contact study subjects. All intervention sessions will be conducted by trained coaches via a HIPAA-compliant video conferencing platform such as Zoom. Assessment data collected will be available only to the project staff and investigators directly involved in with this study. No others will have access to the data. Collected data are confidential. Each subject will be assigned a unique identification number. Direct identifiers including contact information will be stored separately from the data collected through questionnaires, interviews, and assessments. The data cannot identify a subject without having access to the link between the identification number and the direct identifiers. A study subject cannot be identified by anyone except the UW lead researchers and authorized research staff members who have legitimate access to the single record identifying subjects by their research ID number. This record will be stored and maintained completely separate from all data and other information gathered. All data will be stored in secure computer files and records will be identified by a unique identification number that are assigned by the study. The data files will not contain any identifying information.
- b. All members of the research team will have completed required training in human subjects and HIPAA, including training in data management and confidentiality.
- c. Retention of identifiers and data: We will not destroy any identifiers (or links between identifiers and data/specimens) and data that are part of your research records until after the end of the applicable records retention requirements.

9. Risk/Benefit Assessment

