- a. Anticipated risks: Subjects in the study may be inconvenienced or experience psychological discomfort related to assessment questions including previous experiences of LGBT-specific adverse experiences and everyday discrimination. Subjects may also experience mild physical discomfort related to engaging in new physical exercise activities. These problems have not previously occurred in Drs. [name] or [name]'s studies, and we estimate the risks to be minimal. Subjects are informed that they are free to not answer any question and not to participate in any exercises.
- b. Protections against psychological discomfort: To minimize the risk of distress or emotional upset, the following steps will be taken: A) The PIs are experienced in conducting interviews and assessments by phone and in-person with subjects experiencing cognitive impairment and mood or behavioral disturbance; they are also experienced with research involving LGBT older adult health. Throughout the study they

will respond in a sensitive and respectful manner, in-person or by phone, to individuals who are distressed. B) The coaches will receive training from the PIs to monitor for distress and will be advised to immediately contact the PIs with any concerns related to the intervention or assessments resulting in psychological discomfort to the subjects. All concerns will be addressed in collaboration with the PIs. Subjects will be advised of their right to not answer any question(s) and/or to withdraw from the study at any time. No adverse emotional responses have been reported in our prior experience with training staff to deliver behavioral strategies. All sensitive questions in the proposed study are worded respectfully and have been used in previous studies with no adverse consequences. C) The coaches and assessment staff receive training on how to monitor for distress and how to identify and monitor potential triggers and redirect participants to other activities with more pleasant memories. D) If psychological distress is identified, for example severe depression or anxiety, referral to a primary care provider or mental health provider will be initiated. Resources (e.g. contact information of participants primary doctor or mental health provider) will be identified at the beginning of the intervention. Distress requiring referral has never occurred in previous studies of the intervention.

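### All three efficacy outcomes are self-reports to a telephone interviewer who is neither masked after treatment nor stated to be separate from allocation and intervention contact

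*Combined protocol and SAP*

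**What the plan says.** Section 4e of the combined protocol and SAP describes the post-treatment measurement: "The UW research staff will conduct, via telephone, a post-treatment assessment after all sessions are completed". It names no role. Section 4b is more specific for baseline, where participants complete "a 40-minute telephone assessment with either the study research coordinator or research study assistant".

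Section 5 lists three efficacy outcomes, each measured at baseline and 7 weeks:
- physical activity, from two recall questions about exercise in the past month
- physical functioning, from the 10-item SF-36 subscale
- quality of life, from the "Quality of Life-AD scale assessed via interviews with participants"

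Under section 4d the control group continues routine medical care and receives no exercise or behavioral training, so participants will know which arm they are in.

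On staffing, section 6b says that names and contact details "will be accessed by research staff to contact participants regarding the intervention and to schedule pre and post treatment assessments with participants". Section 8a says "All intervention sessions will be conducted by trained coaches". Section 9b(C) says "The coaches and assessment staff receive training on how to monitor for distress". Section 7a adds that "the study assessment staff will schedule a virtual consent visit using Zoom".

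From the objectives onward, no section mentions masking or blinding of anyone, and none says who holds the allocation. The opening page was not available to check. Section 10 tests initial efficacy by ANCOVA and uses the resulting effect sizes and confidence intervals to size the next study.

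**The concern.** When the outcome is an answer given in conversation, the interviewer is part of the measurement. Someone who knows that the respondent has just completed an exercise program may clarify a question differently, accept a first answer more or less readily, or settle a hesitant reply in one direction. The respondents have early stage memory loss, and the activity outcome asks them to estimate typical daily hours and number of days over a month, so some clarification is likely.

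An interviewer effect that differs by arm at the post-treatment call would not be removed by adjusting for baseline. It would sit inside the estimated treatment effect. It would affect the efficacy test and, through the effect sizes, the sample size of the next trial.

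**Working it through.** **Step 1: who does what.** The plan gives no figure on this point, so the check begins by setting the sections side by side.

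| Task | Who, according to the protocol | Section |
|---|---|---|
| Baseline call | research coordinator or research study assistant | 4b |
| Post-treatment call | UW research staff, role not named | 4e |
| Contact about the intervention | research staff | 6b |
| Scheduling of both assessments | research staff | 6b |
| Intervention sessions | trained coaches | 8a |
| Scheduling of the consent visit | assessment staff | 7a |
| Focus-group and workshop invitations | not named; both follow the post-treatment assessment | 4c, 4d |
| Holding the allocation | not stated | none |

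Coaches deliver the sessions, and section 9b(C) names them separately from assessment staff, so nothing suggests that a coach makes the outcome call. What remains open is whether the interviewer also handles intervention contact or sees the allocation. One label covers the post-treatment call, intervention contact and assessment scheduling, and no sentence separates them. Section 4 also lists assignment (4a) before the baseline call (4b), so both baseline roles may know the arm early.

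**Step 2: an illustration of size.** Inputs from the documents: 15 per arm (section 4a) and ANCOVA (section 10). Assumptions, because the documents give no values: two-sided alpha 0.05, no dropout, outcome SD scaled to 1, true effect zero, and a bias of b SD favoring the intervention at the post-treatment call only.

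For an unadjusted t-test:
- standard error of the difference = √(2/15) = 0.365
- noncentrality = b / 0.365, which is 0.27, 0.55 and 0.82 for b = 0.1, 0.2 and 0.3
- rejection rate = probability that a noncentral t with 28 degrees of freedom falls outside the two-sided 5% limits

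For ANCOVA with baseline correlation r, the SD becomes √(1 − r²) and the degrees of freedom 27. The bias stays the same while the standard error shrinks, so the rejection rate is higher.

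| Assumed bias | Unadjusted | ANCOVA, r = 0.5 | ANCOVA, r = 0.7 |
|---|---|---|---|
| 0 | 5.0% | 5.0% | 5.0% |
| 0.1 SD | 5.8% | 6.1% | 6.6% |
| 0.2 SD | 8.3% | 9.4% | 11.5% |
| 0.3 SD | 12.5% | 15.0% | 19.9% |

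**Step 3: carry-over to the next study.** Section 10 speaks of a medium effect without a number; 0.5 SD is assumed here. By the normal approximation, a trial planned on 0.5 SD at 80% power needs 2 × (1.96 + 0.84)² / 0.5² ≈ 63 per arm. If part of the observed 0.5 SD is bias, the power of that trial for the remaining true effect is:
- 0.1 SD of bias, true effect 0.4: Φ(0.4 × √(63/2) − 1.96) ≈ 61%
- 0.2 SD of bias, true effect 0.3: Φ(0.3 × √(63/2) − 1.96) ≈ 39%

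**The case against.** The strongest reply is that this is a 30-person pilot whose enrollment and adherence proportions do not depend on these interviews, and that the instruments leave little room for interviewer influence: 3-point SF-36 items, 4-point QoL-AD items and two numeric questions. Participants are at an early stage and can consent for themselves. They also know their arm and report every outcome, so a masked interviewer leaves their own reporting bias untouched, and some will reveal the arm anyway.

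Much of this stands. It limits both the likely size of the bias and what masking can achieve. It does not remove the concern, because section 10 still tests efficacy and carries the effect sizes forward.

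A reader might also infer three stronger claims, which the documents do not support:
- **That the same people handle the intervention and collect the outcomes.** Section 6b is a data-access statement using a generic label, and sections 8a and 9b(C) distinguish coaches from assessment staff. The supportable statement is that separation is not specified.
- **That two named assessors make masking certain without extra staff.** The two roles are given for baseline only, and nothing shows that either is unaware of the allocation.
- **That the interviewer is the only place where bias can be reduced.** Self-completion or an objective activity measure would also reduce interviewer influence, and section 7a already uses REDCap for electronic consent.

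**Conclusion.** The concern holds as an unaddressed and largely avoidable source of bias, and the protocol should deal with it. The documents establish that every efficacy outcome is a self-report by telephone, that participants know their arm, and that no provision masks the post-treatment interviewer or separates that person from allocation and intervention contact. They do not establish that bias will occur or how large it would be.

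The figures above are illustrations. At an assumed 0.1 SD the rejection rate barely moves; at 0.2 to 0.3 SD the rise is material, and more so under the planned ANCOVA if baseline and follow-up are well correlated. The feasibility and acceptability aims are unaffected. The matter bears on the efficacy comparison and on planning the next study.

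**What to change.** In section 4e, state that:
- The week-7 call is made by an existing assessment staff member, for example whichever of the coordinator or assistant has had no intervention contact with that participant, working from a call list without group assignment.
- The call opens with a scripted request not to mention the group. The script must not limit the reporting of distress, which assessment staff are trained to monitor under section 9b(C).
- Other staff make the focus-group and workshop invitations. Their timing after the assessment is already set in sections 4c and 4d; only the person needs specifying.
- The interviewer records after each call whether the group became known, so that the extent of unmasking can be reported.

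If existing staff cannot be separated in this way, say so and state unmasked outcome assessment as a limitation when interpreting efficacy and when using the effect sizes for planning.

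The cost is a division of tasks, a short script and one recorded item per call, with less scheduling flexibility as the main downside. The report should acknowledge that participants' own reporting bias remains and that some participants may disclose their arm.
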